Visit 4: All procedures as in visit 2 will be performed again, including dietary recall, targeted physical exam, and sample collection. All subjects will also get another oral FMT/placebo dose of 5 capsules each depending on their original assignment. All subjects in the study will get this intervention unless (a) they refuse the intervention (b) have undergone a liver transplant or have died/discharged to hospice (c) developed an infection or an SAE that was adjudicated to be related to FMT in the interim or (d) are currently undergoing antibiotic therapy for an infection that is not related to FMT.

For those who are infected due to an FMT-unrelated infection, we will approach the patients 2 days after the completion of the assigned antibiotic course. For those initiated on SBP (Spontaneous Bacterial Peritonitis) prophylaxis, we will provide the intervention after the initial SBP episode is treated. This may require delaying the intervention from day 30 to up to day 45 but this will still be counted as the second FMT.

All other subjects will be given the intervention and the blind will still be maintained. The brain function tests and QOL will be performed again. Groups 1 and 2 will get active FMT and groups 3 and 4 will get placebo FMT. No enemas will be given. The subjects will then be sent home.

Follow-up visits every month: The subjects will be followed monthly in person, or by phone or videoconference at Months 3, 4, 5 to evaluate dietary and medication changes and for safety analysis (hospitalizations, AEs or SAEs), targeted physical exam and for collection of samples at each study clinic visit. Mail-in kits for collection of stool, and urine will be provided along with instructions for use if visit is performed remotely. We will also perform the cognitive tests and QOL assessment at one month post-second intervention and at 6 months. We will continue to follow every patient for 6 months regardless of whether they developed an SAE or hospitalization in between. Only reasons not to follow them up for 6 months would be death, liver transplantation or patient withdrawal of consent.

End-of-Study visit: Per FDA mandates for FMT studies, we will see the patients at six months and we will evaluate AEs, interim hospitalizations, dietary recall, and perform targeted physical exam, QOL and brain function studies, and collect serum, and stool again. At this point the participation of the patient will end.

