Specific safety findings will result in temporarily suspending enrollment until a safety review is convened, the objective of which is to determine whether the study should continue per protocol, proceed with caution, be further investigated, be discontinued, or be modified and then proceed. Suspension of enrollment is another potential outcome of a safety review. This will be done if the assigned infection is in the FMT group since this patient population is prone to infections.

Subsequent review of serious, unexpected, and related AEs by the Data and Safety Monitoring Board, IRB, the PI, or the FDA or relevant local regulatory authorities may also result in suspension of further trial interventions/administration of FMT at a site. The FDA and PI retain the authority to suspend additional enrollment and study interventions/administration of FMT for the entire study, as applicable. The PI and the adjudication panel will make the initial decision. The subsequent safety review by the IRB and FDA will then decide if the study can resume.

Findings that will trigger a safety review are

Findings that will trigger a safety review are

- o Death related to FMT material or study procedures in any subject;
- New potentially transmitted infection in five or more subjects assigned to FMT - i.e., cannot exdude transmission and/or attribution is

pending investigation/Data Monitoring Committee (DMC) adjudication;

- Any single potential transmitted infection assessed as possibly, probably, or definitely related to FMT by the investigator and DMC.
- One or more subjects assigned to FMT has a serious, unexpected AE assessed as possibly, probably, or definitely related to FMT by the investigator and DMC; Five or more subjects (per assigned group) develop a new diagnosis of a medical condition or immune-mediated disease considered probably, or definitely related to FMT.
- Five or more severe AEs of a similar nature occurring in different subjects and assessed as definite, possible or probable relatedness to study product in groups assigned to FMT (per assigned group)

FDA/CBER will be notified by phone or fax within 72 hours if the study is halted for review.

Individual study halting rules

- (1) patient's choice
- (2) change in GI adverse events with a magnitude of 3 increase over baseline
- (3) fever and signs of infection (including WBC count >12,000/ml)
- (4) SAE development including cirrhosis complications (OHE) and hospitalizations for

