- any cause including bleeding, nausea, vomiting, or other GI conditions
- (5) increase in MELD score by 8 or more
- (6) Increase in AST, ALT or Alkaline phosphatase to 10X ULN
- (7) Non-elective Hospitalization

Even if the subject is withdrawn before 30 days, they will still be followed till 6 months for safety.

Health risks (please see adverse events table attached):

Adverse events will be both for the FMT material, placebo as well as for the procedures. These risks are listed in the Risk Section of the informed consent.

These possible adverse events will be:

- (a) Fever: yes or no answer with grading based on actual temperature on examination
- (b) diarrhea (will be asked to grade them from 0-4 compared to baseline)
- (c) abdominal cramping and pain (will be asked to grade them from 0-4 compared to baseline)
- (d) vomiting (will be asked to grade them from 0-4 compared to baseline)
- (e) Development of HE (Altered mental status) in every group: will be monitored by clinical examination through the West-Haven Criteria²⁵. We will be closely monitoring all subjects for this development, including a clinical examination by a gastroenterologist at every visit.

(f) Development of infections specifically spontaneous bacterial peritonitis -Fever will be reconfirmed by measuring by the study nurse and if it is confirmed, a detailed investigation into the cause of the fever will be performed as part of standard clinical care and the patient will be withdrawn from the study.

-Vomiting, constipation, GI bleeding, abdominal cramps and diarrhea: If the patient's diarrhea and abdominal cramps change in a magnitude of 3 over their baseline values per the AE chart (patients with cirrhosis often have these symptoms at baseline), they will be withdrawn from the study.

-Infections that occur in the FMT group will be thoroughly investigated according to standard clinical care to prove whether they were associated with the FMT.

Adverse Event Grading Chart

 Volunteer Study ID:
 Date:
 Time:

 Study Start Date:
 Current Visit number:

*Volunteer's responses will be marked on grading sheet by circling the appropriate grade or indicating no symptoms.

PARAMETER COMPARED TO BASELINE	GRADE 1 MILD	GRADE 2 MODERATE	GRADE 3 SEVERE	GRADE 4 POTENTIALLY LIFE-THREATENING
ESTIMATING SEVERITY	(GRADE		•	•

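### After an SAE or infection before day 30, the Visit 4 text and the individual halting rules give opposite instructions on the second oral dose, and nothing says which governs

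*Combined protocol and SAP*

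**What the plan says.** **Visit 4 (Procedures).** All subjects receive a second set of five capsules, FMT in Groups 1 and 2 and placebo in Groups 3 and 4. There are four exceptions: (a) refusal; (b) transplant, death or hospice; (c) the subject "developed an infection or an SAE that was adjudicated to be related to FMT in the interim"; (d) current antibiotics for an infection not related to FMT. Subjects under (d) are approached two days after the antibiotic course ends. The text adds: "For those initiated on SBP (Spontaneous Bacterial Peritonitis) prophylaxis, we will provide the intervention after the initial SBP episode is treated". The delay may run to day 45.

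**Individual study halting rules.** Rule (3) is "fever and signs of infection (including WBC count >12,000/ml". Rule (4) is "SAE development including cirrhosis complications (OHE) and hospitalizations for" any cause. Rule (7) is "Non-elective Hospitalization". None mentions relatedness. The section closes: "Even if the subject is withdrawn before 30 days, they will still be followed till 6 months for safety".

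**Health risks.** Once a fever is confirmed, its cause is investigated "as part of standard clinical care and the patient will be withdrawn from the study".

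**Visit 3 (day 15).** Continuing in the study is made conditional on no AE or SAE having occurred, again without a relatedness test.

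**Follow-up visits every month.** Every patient is followed for six months whether or not an SAE or hospitalization occurs. This settles follow-up, not dosing.

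**The concern.** The enema and the first capsules are given together at Visit 2, and safety follow-up continues after withdrawal. The second oral dose is therefore the only study treatment that an individual halting rule can stop. For a patient with an unrelated OHE episode, treated spontaneous bacterial peritonitis (SBP) or an unplanned admission in the first month, the site can read one section as an instruction to dose and another as an instruction to stop.

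The Visit 4 text also has a gap of its own. Exception (c) applies to events already adjudicated as related. A subject whose OHE or other non-infectious SAE is still under review falls outside it and, as written, is dosed. The Adjudication section has the DMC meet three times a year, and no section sets a deadline for a relatedness decision, so an event in the first month could well be open at Visit 4.

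At stake are re-exposure to active capsules in Groups 1 and 2 after a serious event, inconsistent handling between similar patients, and a second-dose record that is hard to interpret. OHE is not a side issue: HE recurrence is named in the primary endpoint.

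**Working it through.** **Step 1. The rules side by side, for events before the second dose.**

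| Event | Visit 4 text | Halting rules and Health risks |
|---|---|---|
| OHE, adjudicated unrelated, recovered | dose | stop, rule (4) |
| Unplanned admission, adjudicated unrelated | dose | stop, rules (4) and (7) |
| SBP with fever, unrelated, treated | dose after treatment, up to day 45 | stop, rule (3) and the fever withdrawal; also (4) and (7) if admitted |
| SAE, relatedness pending, no antibiotics | dose | stop, rule (4) |
| SAE adjudicated related | withhold | stop, rule (4) |

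Only the last row agrees. The Visit 3 condition would also stop the subject in any row where the event falls before day 15. The conflict has a limit: rule (3) needs fever and signs of infection, so an infection without these, without admission and not counted as an SAE is simply deferred and dosed under Visit 4.

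**Step 2. Whether any text ranks the rules.** There is no cross-reference in either direction. Visit 4 does say "All procedures as in visit 2 will be performed again", and Visit 2 opens with re-confirming eligibility. If that re-check carries over, exclusion G (non-elective hospitalization in the last month) would catch an admission since baseline at day 30. But Visit 4 lists its own exceptions. For a day-45 dose, a one-month window reaches back only to about day 15 (45 − 30), so an earlier admission would pass. The re-check adds a third reading and ranks nothing.

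**Step 3. Scale.** The plan gives no figure for halted subjects or omitted doses. The nearest inputs are in the Sample size section: 25 per group and six-month hospitalization rates of 10% (Group 1), 30% (Group 2), 30% (Group 3) and 80% (standard of care, taken here for Group 4). A four-group chi-square power calculation at these rates gives 99.7%, 98.8% and 94.9% for 25, 20 and 15 per group. The plan states 100%, 98% and 94%, so the rates are being read as the sponsor used them.

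The timing of admissions is not given and has to be assumed. Expected first admissions by day 30 of 180:

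- Even spread, 25 × p × 30/180: 0.42, 1.25, 1.25, 3.33; total 6.25.
- Constant hazard, 25 × (1 − (1 − p)^(30/180)): 0.44, 1.44, 1.44, 5.88; total 9.20.

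Groups 1 and 2, who would receive active capsules: 0.42 + 1.25 = 1.67, or 0.44 + 1.44 = 1.88.

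Sensitivity: with a 50% placebo rate, Group 4 contributes 2.08 to 2.73 and the total is 5.00 to 6.05. If 25% of those admitted were already withheld or deferred by Visit 4 (assumed), 4.69 to 6.90 remain; if 50%, 3.12 to 4.60.

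**The case against.** The best defence is that the Visit 4 wording, which speaks of subjects in the study, already leaves out anyone halted. The text does not say so. On that reading the relatedness test for SAEs in exception (c) would have nothing to do, because every SAE would already have stopped the subject, and the SBP sentence would have almost nothing to do.

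A second defence is that other safeguards cover the dangerous cases, and part of it stands. For a suspected transmitted infection, donor material is quarantined during the investigation (Specific investigation of the infection), and each active subject's material must come from one donor (Number of interventions). Active re-dosing is thus already limited there. This does not reach OHE or other non-infectious SAEs. If eligibility is re-checked, exclusion F and safety-related items (9) and (12) bar dosing during infection, during acute illness or fever, or where the investigator judges it unsafe. The PI and FDA can also suspend interventions. These limit harm; they do not tell the site which written rule applies.

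A reader might infer more than the documents support:

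- *That a hold on pending events would unblind the arm.* The plan contains no such hold. The DMC relatedness referral in Safety and hospitalization analysis covers all FMT-randomized groups, so a hold tied to it would show only that the subject is not in Group 4, and not whether the capsules are active.
- *That applying the halting rules would bias the second-dose comparison in secondary aim 5, because omitted doses would be mostly placebo.* That imbalance comes from the assumed 80% and 10% rates in Groups 4 and 1. With no treatment effect the expected split is even.
- *That the DMC must decide within a fixed number of days.* No section sets a limit for relatedness decisions.

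**Conclusion.** The inconsistency is real and rests on the text alone. Visit 4 withholds the second dose outright for an SAE or infection only when it has been adjudicated as FMT-related. Halting rules (3), (4) and (7), the confirmed-fever withdrawal and the Visit 3 condition have no relatedness test, and no sentence sets the order of precedence. The pending-event gap is a separate defect within Visit 4, mainly for OHE and other non-infectious SAEs. Either policy is defensible; leaving both in force is not.

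The number affected is probably small. About 6 to 9 of 100 subjects admitted by day 30, about 2 of them in Groups 1 and 2, is an illustration under the planning rates and assumed timing. It might be read as a maximum, but it is neither a maximum nor a minimum. It omits outpatient OHE and the fever, GI, MELD and liver-enzyme triggers, for which the plan gives no rates. It includes some subjects whom Visit 4 already withholds or defers. Exclusion G may also lower early admission risk below a constant hazard. The sponsor should correct this, but it does not undermine the trial.

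**What to change.** 1. State in Visit 4 and in the individual halting rules which governs the second dose, and align Visit 3 and the fever sentence in Health risks. There are two coherent choices:
   - **Halting rules govern.** A subject meeting rules (2) to (7) before the second dose does not receive it, in any group. The deferral and SBP text in Visit 4 must then be cut back, because this choice largely nullifies it. The Stop-points section counts the listed infections, SBP among them, with serious events in the FMT group, so rule (4) would catch most of them.
   - **Visit 4 governs.** Rules (3), (4) and (7), the fever withdrawal and the Visit 3 condition exempt, for the second dose, events adjudicated as unrelated.
2. If re-dosing after unrelated events is kept, hold the second dose in all four groups while relatedness of an SAE or infection is pending, and omit it if unresolved by day 45. The referral wording under Assessment of Causality is broad enough to serve all groups. Under the first choice this hold is unnecessary for SAEs, which already stop the dose.
3. Analyse by randomized group, and report second-dose receipt and the reason for each omission by group.

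The cost is a few sentences in four places, a few omitted or delayed second doses and, under the second choice, occasional relatedness decisions outside the DMC's three meetings a year. Those decisions are a real demand on a centralized committee and should be agreed with it in advance.

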1. Study procedure-related adverse events from enema (e.g. perforation, bleeding, etc.)

- 2. FMT material-related adverse events (e.g. transmissible infection, allergic reaction)
- 3. Capsule ingestion-related adverse events (pill-associated dysphagia)

4. Short-term safety: Both solicited and unsolicited adverse events will be recorded by, clinical assessment at all in-person visits. The subjects will have the ability to telephone the study team at any point during the study.

5. Long-term safety: follow-up monthly till 6 months to evaluate for SAEs (listed below).

Solicited AEs throughout the trial will be

- (a) fever:
- (b) diarrhea
- (c) vomiting
- (d) constipation
- (e) GI bleeding
- (f) abdominal cramping and pain
- (g) Development of HE (confusion/altered mental status):
- (h) Development of infections, specifically spontaneous bacterial peritonitis
- (i) New onset or significant worsening of chronic medical conditions
- (j) New potentially transmitted infections

We do not expect the infections to occur at a higher rate than the natural history of cirrhosis at this stage. This is borne out by our enema study, in which the FMT group had no infections. Also, a nasojejunal study performed by Phillip et al in severe alcoholic hepatitis, whose MELD scores were much higher than our proposed patients, did not reveal a poor safety profile. We will monitor for all infections and specifically for spontaneous bacterial peritonitis (SBP).

All safety assessments in FMT will be compared to placebo groups given the advanced nature of the cirrhosis and the association of several of these symptoms in the natural history of the disease

Stop-points or reportable adverse events

Any hospitalization or event that is life-threatening will be deemed a serious adverse event in the FMT group and reported to the IRB, FDA, DMC and Molecular and Cellular Therapeutics (GMP) facility at the University of Minnesota within 72 hours (per usual protocol).

This will include the development of an infection that is gut-based/not gut-based:

Gut-Related

- Spontaneous Bacterial peritonitis
- Infectious diarrheal illnesses

Others

- UTI
- Respiratory
- Skin/soft-tissue
- Bacteremia

Overall Study Halting Rules

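### The Visit 4 second-dose rule and the individual halting rules conflict after an FMT-unrelated infection, SAE, OHE episode or unplanned admission, and no text says which governs

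*Combined protocol and SAP*

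**What the plan says.** All references are to the combined protocol and SAP.

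**Procedures, Visit 4** makes the second oral dose the default. The exceptions are (a) refusal; (b) transplant, death or hospice; (c) a subject who "developed an infection or an SAE that was adjudicated to be related to FMT in the interim"; and (d) current antibiotics for an unrelated infection. Exception (d) only postpones the dose: "we will approach the patients 2 days after the completion of the assigned antibiotic course". For subjects started on SBP prophylaxis, "we will provide the intervention after the initial SBP episode is treated". The delay may run to day 45. The section then closes the list: "All other subjects will be given the intervention and the blind will still be maintained".

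**Individual study halting rules** include (3) "fever and signs of infection (including WBC count >12,000/ml"), (4) "SAE development including cirrhosis complications (OHE) and hospitalizations for" any cause, and (7) "Non-elective Hospitalization". None mentions relatedness to FMT. The sentence after the list keeps subjects withdrawn before Day 30 in safety follow-up to 6 months. **Health risks** adds that a subject whose fever is confirmed is withdrawn.

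**Exclusion criterion G** bars anyone with an unplanned admission in the previous month. Visit 4 repeats the Visit 2 procedures, and Visit 2 opens with a re-check of eligibility.

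**The concern.** For the same event, one section tells staff to give the capsules and another tells them to stop the subject. No sentence ranks the two or limits the halting rules to FMT-related events, so the choice falls to staff case by case.

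In Groups 1 and 2 that choice decides whether a patient with cirrhosis who was recently infected or admitted receives more active FMT. In all groups it makes second-dose exposure inconsistent, and secondary aim 5 (microbiota change after the second oral dose) depends on that exposure. The triggering events are expected in this population: HE recurrence is named in the primary endpoint, and OHE is a halting event.

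**Working it through.** **1. The rules side by side**

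| Event before the second dose | Visit 4 | Halting rules and Health risks | Result |
|---|---|---|---|
| Infection or SAE adjudicated FMT-related | withhold | stop | agree, where a halting rule applies |
| Unrelated febrile infection, still on antibiotics | withhold for now | stop: (3), confirmed fever | agree for the moment |
| Unrelated febrile infection, antibiotics finished | re-approach after 2 days, up to day 45 | stop: (3), confirmed fever | direct conflict |
| SBP treated, prophylaxis started | give | stop: (3) if febrile, (4) if an SAE, (7) if admitted | direct conflict |
| Unrelated OHE episode or other SAE | give (closing clause) | stop: (4) | conflict on the natural reading |
| Unrelated unplanned admission | give (closing clause) | stop: (4), (7) | conflict on the natural reading |

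The last two rows rest on exception (c). If every SAE already stopped dosing under rule (4), the SAE part of (c) would never have any effect.

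**2. Inputs for scale**

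The plan gives no figure for this point. The Sample size section gives 6-month hospitalization of 10% for combined FMT, 30% for each single route, and 80% for standard of care, with 25 per group. It states no placebo rate, so 80% is assumed here. That matches how the plan seems to have been powered. A four-group chi-square test (3 df, α = 0.05) with rates 10/30/30/80% has mean rate 0.375 and w² = 0.066875/0.234375 = 0.285 (w = 0.534). It gives power of 99.7%, 98.8% and 94.9% at 25, 20 and 15 per group, against the stated 100%, 98% and 94%.

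**3. Expected admissions by Day 30**

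Timing is not given, so two assumptions are used, with p the 6-month rate.

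- Even accrual, 25 × p/6: 0.42 + 1.25 + 1.25 + 3.33 = 6.25 of 100. Groups 1-2: 1.67. Groups 3-4: 4.58.
- Constant hazard, 25 × [1 − (1 − p)^(1/6)]: 0.44 + 1.44 + 1.44 + 5.88 = 9.20 of 100. Groups 1-2: 1.88. Groups 3-4: 7.32.

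**4. Sensitivity**

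- Placebo at 50%: totals 5.00 and 6.05; Groups 1-2 unchanged.
- No FMT effect (80% in every group): 100 × 0.1333 = 13.3 (even) and 100 × 0.2353 = 23.5 (constant hazard). Groups 1-2 hold half, 6.7 and 11.8.
- To day 45, the limit for a delayed dose, with constant hazard over 182.5 days: about 13 of 100, of whom about 2.8 are in Groups 1-2.

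These counts cover admissions of any relatedness, so they include some FMT-related events on which the rules agree. They omit OHE or infection without admission, for which the documents give no rate. Early clustering of admissions would raise them.

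**The case against.** The best defence is that Visit 4 addresses subjects still in the study, so anyone already halted is outside it and the rules run in sequence. The halting list never says that the second dose is withheld; that consequence is inferred from the withdrawal sentences. The second half of this stands: halting is not defined. The sequence reading, however, fails for treated infection and SBP, where Visit 4 expressly doses afterwards. For SAEs it leaves exception (c) idle. Redundancy is weaker evidence than contradiction, which is why those rows are called a conflict on the natural reading and not a direct one.

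A second defence is that the repeated eligibility check, through exclusion G, withholds the dose after an admission anyway. But the section does not say that a failed re-check bars dosing. The exclusions also cannot all be re-applied: criterion Q (FMT in the last 6 months) would bar everyone given active FMT at baseline. G therefore adds a further inconsistent instruction without settling the matter. The investigator's general discretion to exclude for safety permits withholding but does not rank the rules.

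Several stronger inferences are tempting and not supported:

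- That Visit 3 is a third conflicting rule. It says a subject without an AE or SAE continues; it does not say that any AE ends participation.
- That every SBP is an SAE by definition. Stop-points or reportable adverse events does say "This will include the development of an infection that is gut-based/not gut-based", but in a reporting context, for the FMT group, and it may mean only infections that are life-threatening or lead to admission. The conflict does not need it when SBP is febrile or leads to admission.
- That DMC adjudication cannot work here because of its meeting schedule, or covers FMT groups only. Nothing rules out a vote between meetings, and Assessment of Causality refers all SAEs to the panel without limiting this to FMT groups.
- That actively infected subjects would be dosed. Both rules withhold during antibiotic treatment and diverge only afterwards.

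**Conclusion.** The contradiction is real and should be fixed. It is direct for a treated FMT-unrelated febrile infection or SBP, and present on the natural reading for an unrelated SAE, OHE episode or admission.

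Through admissions alone the scale is about 6 to 9 of 100 subjects by Day 30 at the protocol's rates, about 2 of them due active capsules. It is about 13 to 24 of 100, with 7 to 12 in Groups 1-2, if FMT has no effect. Both ranges rest on assumed timing, a placebo rate of 80% and events of any relatedness, so neither is a bound.

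A reader might infer that the primary endpoint is compromised. The documents do not support that: the follow-up text and the sentence after the halting list keep halted subjects under observation to 6 months. The consequence is confined to second-dose safety and to consistent exposure for secondary aim 5.

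**What to change.** Amend Visit 4 and the individual halting rules (with the fever sentence in Health risks) together, so that one stated rule governs, applied identically and blinded in all four groups. Either version removes the conflict:

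1. After a halting event, withhold the second capsules unless the event has resolved, it is judged unrelated to study product, and the dose can be given by day 45; or
2. The halting rules govern, and the delay paragraph at Visit 4 is deleted.

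In both, say that halting concerns dosing and that follow-up continues to 6 months. State whether exclusion G applies at Visit 4. If it does, version 1 could not be used at Day 30 after an interim unplanned admission. Keep the existing investigator assessment and DMC relatedness process; neither has to change.

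The cost is one amendment. Some subjects may miss the second capsules. Under version 2 the admission route alone would account for roughly the counts above, plus an unquantified number with OHE or infection and no admission. Version 1 would lose fewer.
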